The following criteria should be met to define UTI: 1. Symptoms of dysuria, urgency, frequency, or hematuria, fever, flank pain, nausea/vomiting; AND 2. Pyuria and/or bacteriuria²⁶. The following criteria should be met to define sepsis: 1.Temperature >38°C or <36°C Heart rate >90/min Respiratory rate >20/min, PaCO2 <32 mm Hg (4.3 kPa), White blood cell count >12 000/mm3 or <4000/mm3 or >10% immature bands, or evidence of organ failure; AND 2. urinary pathogen growth in urine or blood cultures²⁷. The EAU classifies UTI as Localised or Systemic. Localised UTI is defined as signs and symptoms of frequency, urgency, Incontinence, urethral purulence, and suprapubic pain, which applies to both sexes, and with no signs of systemic infection. Systemic UTI is defined as signs and symptoms of systemic infection such as fever or hypothermia, chills, Delirium, Hypotension, Tachycardia, and Costovertebral angle pain and tenderness. Pyelonephritis and prostatitis are included in this classification.

The prevalence of Prostatitis is 8.2%. Prostatitis is classified into four clinical entities including acute bacterial prostatitis, chronic bacterial prostatitis, chronic pelvic pain syndrome and asymptomatic prostatitis. Diagnostic evaluation includes history and physical examination, urinalysis, urine gram stain and culture, pre- and post-prostatic massage, and Prostate specific Antigen. Complete Blood Count, Blood culture is not routinely done, but may be necessary in a patient who appears ill²⁸.

Acute Bacterial prostatitis is defined as bacterial infection of the prostate which may lead to overwhelming sepsis or development of prostatic abscess. An organism must be isolated on culture. Most commonly isolated organism is E. Coli. Diagnosis is based on symptoms alone which include irritative and/or obstructive symptoms. Pain and systemic symptoms may be present as well. On physical examination, prostate appears boggy, tender, and enlarged. Diagnosis is made through a urinalysis and urine culture. Presence of more than 10 WBCs per hpf suggests a positive diagnosis. It is usually treated with antibiotcis²⁸.

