Patients experiencing an adverse event such as symptoms of urinary tract infection like hematuria, dysuria, frequency, and urgency and systemic symptoms such as fever, generalized weakness, malaise will be evaluated right away initially with a complete blood count, urinalysis, and urine culture. Patients who will satisfy the criteria of Urinary Tract Infection, will be considered as having post biopsy infectious complications, and will be evaluated for possible sepsis. According to literature, 2% of patients undergoing prostate biopsy may experience mild post biopsy infection. 1% of patients may develop severe infections or urosepsis requiring hospitalization²². Computed sample size for the study is a total of 120 patients, with 60 patients in each arm. Hence, if more than 2 patients develop mild biopsy infection, and more than 1 patient develop severe infections from the experimental group, the study will be terminated and conclusion will be recommendation of administration of antibiotic prophylaxis. Patients who were not able to complete the procedure due to any circumstance, those who cannot tolerate anesthesia, those with adverse effects from anesthesia or antibiotics, and patients not compliant to follow up tests will be withdrawn from the study.

Data to be gathered

Patients who will pass the inclusion criteria will have their demographic data recorded such as age, sex, Height, Weight, BMI, Charlson Scores, Prostate volume, PSA, and History of Previous Biopsies. Post operatively, UTI will be assessed using a symptom checklist, which includes dysuria, urgency, frequency, or hematuria, fever, flank pain, nausea/vomiting. Signs of Systemic Inflammatory Response Syndrome (SIRS) will be gathered in patients who develop signs of urinary tract infection, namely, Temperature, Heart Rate, Respiratory Rate, White Blood Cell Count, and Blood Pressure. Incidence of sepsis and UTI In both groups will be recorded. Patients with Fever, or 2 or more signs of SIRS will be advised admission immediately. Histopathology results, 30 day readmissions, 30 day emergency room visit, and non infectious complications based on the Clavien Dindo classification will also be gathered.

Laboratory/assessment procedures to be performed

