Patients with adverse effects will be followed until resolution or stabilization. A cut-off of 30 days was chosen because the vast majority of post-biopsy infections will occur within this time period. A standard data collection form will be used and information will be recorded in a password protected Excel spreadsheet. Any time post biopsy, patients may call the primary investigator to have them properly assessed and advised, in coordination with consultants on board the study, and possible a referral to infectious disease service for treatment planning. Treatment costs will be shouldered by the study as part of indemnification. A budget proposal will be submitted to cover for treatment costs. For patients with mild symptoms which may be treated as outpatient, a budget of 10,000 pesos per patient will be given.

[figure not shown]
Description of Outcome Measures

Primary outcome is the incidence of Urinary tract infection and Sepsis. Urinary tract infection is based on the European Association of Urology guidelines on infection. Localized UTI is defined as having symptoms of Dysuria, Urgency, Frequency, Incontinence, and Pressure or cramping in the lower abdomen. Systemic UTI is defined by the presence of localized symptoms plus one of the following: Fever or hypothermia, Rigors, shaking or chills, Delirium, Hypotension, Tachycardia, and Costovertebral angle pain and tenderness. Mild, and Self-limiting lower urinary tract symptoms such as hematuria and dysuria which spontaneously resolves will not be assessed as urinary tract infection, as these are commonly seen after prostate biopsy and rarely require treatment.

Secondary outcome includes the following: 30 day hospital admissions, 30 day emergency room visits, and non-infectious complications such as acute urinary retention will be recorded.

Sample Size and Sampling Technique

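### The UTI checklist does not carry the signs that define the primary outcome, and vital signs and sepsis assessment follow only after UTI is suspected or met, so some events may be missed or misclassified

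*Protocol*

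**What the plan says.** **Outcome (Protocol, Description of Outcome Measures).** "Primary outcome is the incidence of Urinary tract infection and Sepsis". For the local form, "Localized UTI is defined as having symptoms of Dysuria, Urgency, Frequency, Incontinence, and Pressure or cramping in the lower abdomen". For the systemic form, "Systemic UTI is defined by the presence of localized symptoms plus one of the following". Seven signs are then named: a raised or a low temperature (counted here as two), rigors or chills, delirium, low blood pressure, a fast heart rate, and pain at the costovertebral angle. Mild, self-limiting symptoms such as hematuria and dysuria are not counted.

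**Data collection (Protocol, Data to be gathered).** "UTI will be assessed using a symptom checklist, which includes dysuria, urgency, frequency, or hematuria, fever, flank pain, nausea/vomiting". A further sentence sets a condition on the vital signs: "Signs of Systemic Inflammatory Response Syndrome (SIRS) will be gathered in patients who develop signs of urinary tract infection". The measurements it names are body temperature, pulse, breathing rate, white cells and blood pressure.

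**Background criteria (Protocol, Background Information and Brief Literature Review).** UTI is defined there by the same seven symptoms as the checklist, plus pyuria and/or bacteriuria. Sepsis is defined by abnormal temperature, heart rate, respiratory rate, PaCO2 or white cell count, or organ failure, together with "urinary pathogen growth in urine or blood cultures". No local urinary symptom is required. This section also summarises the European guideline's systemic UTI without stating that local symptoms must be present.

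**Route to a sepsis evaluation (Protocol, Criteria for withdrawing subjects).** Men with urinary or systemic symptoms get a blood count, urinalysis and urine culture. Those who then satisfy the UTI criteria are evaluated for possible sepsis.

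**The concern.** A form that feeds a primary outcome should put every defining sign to every patient in the same way. Here the form and the outcome appear to come from different definitions, so two gaps follow.

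- **Missing items.** A man whose only local symptom is incontinence or lower-abdominal cramping has no matching item. A man with dysuria and rigors, but no fever or other listed sign, has no named item that makes him a systemic case.
- **Conditional collection.** Temperature, heart rate, respiratory rate, white cell count and blood pressure are gathered only once signs of UTI are present, and sepsis is evaluated only in men who meet UTI criteria. Sepsis is half of the stated primary outcome and, by the protocol's own criteria, can occur without a local symptom. The urine culture that supplies one limb of those criteria is taken in everyone at day 7. The vital signs that supply the other limb are not specified for everyone.

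At stake is the ascertainment of a rare outcome in a non-inferiority comparison, where a handful of events decides the result.

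**Working it through.** **Step 1. Set the lists side by side.** Fever and hypothermia are counted separately, and flank pain is credited as matching costovertebral angle pain.

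| Outcome sign | Checklist | Vital signs, once UTI is suspected |
|---|---|---|
| Dysuria | yes | – |
| Urgency | yes | – |
| Frequency | yes | – |
| Incontinence | no | no |
| Lower-abdominal pressure or cramping | no | no |
| Fever | yes | yes |
| Hypothermia | no | yes |
| Rigors or chills | no | no |
| Delirium | no | no |
| Hypotension | no | yes |
| Tachycardia | no | yes |
| Costovertebral angle pain | near match | – |

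Total: 5 on the checklist + 3 recovered only through the conditional vital signs + 4 in neither = 12. In the other direction, two of the seven checklist items (hematuria, nausea/vomiting) do not define the outcome. Both are in the background UTI criteria.

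**Step 2. What the condition on vital signs can lose.**
- *Systemic UTI.* The outcome requires local symptoms, so taking vital signs after signs of UTI does not in itself lose a systemic UTI. It can do so through the two unlisted local symptoms, if those fail to trigger collection.
- *Sepsis.* No local symptom is required, so here the condition matters directly. Fever is on the checklist and prompts a work-up, as do weakness and malaise. The gap is therefore mainly afebrile or hypothermic sepsis without local symptoms.

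**Step 3. The planned size, for context.** Inputs from Sample Size and Sampling Technique: 1.35% with prophylaxis, 1.22% without, margin 5%, power 80%, 90% interval (one-sided 0.05).

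n = [0.0135×0.9865 + 0.0122×0.9878] × (1.645 + 0.842)² / (0.05 + 0.0013)² = 59.6, so 60 per arm.

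The stated 60 reproduces and is unaffected by this point. Expected events: 60 × 0.0135 = 0.81 and 60 × 0.0122 = 0.73. One case is 1/60 = 1.7 percentage points.

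**Step 4. How far one missed case moves the verdict.** The protocol passes if the upper 90% bound is below 5% but does not give the interval formula. Two are shown as assumptions.

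- Wald: d + 1.645 × √[pA(1−pA)/60 + pB(1−pB)/60]
- Newcombe: d + √[(uA−pA)² + (pB−lB)²], where l and u are the 90% Wilson limits of each arm

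Here d = pA − pB, and A is the arm without prophylaxis.

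| Method | Missed case in | True events, A v B | Upper bound | Recorded events, A v B | Upper bound |
|---|---|---|---|---|---|
| Wald | A | 2 v 1 | 1.67 + 1.645×2.846 = 6.35% (fails) | 1 v 1 | 0 + 1.645×2.337 = 3.84% (passes) |
| Wald | B | 2 v 3 | −1.67 + 1.645×3.645 = 4.3% (passes) | 2 v 2 | 0 + 1.645×3.277 = 5.4% (fails) |
| Newcombe | A | 1 v 1 | 0 + √(5.46² + 1.29²) = 5.6% (fails) | 0 v 1 | −1.67 + √(4.31² + 1.29²) = 2.8% (passes) |
| Newcombe | B | 1 v 2 | −1.67 + √(5.46² + 2.22²) = 4.2% (passes) | 1 v 1 | 5.6% (fails) |

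Under either formula a single case can reverse the verdict, and the direction depends on the arm.

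**Step 5. Equal misses in both arms.** If a fraction s of true events is recorded in each arm, the expected difference is s×pA − s×pB = s×(pA − pB). Any s below 1 shrinks a true difference towards zero, which favours non-inferiority when omission is truly worse.

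**The case against.** The strongest case is that the checklist is not the only route to an event.

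- It is introduced as a list that includes these items, not as a closed one.
- Laboratory/assessment procedures and Follow-up procedures provide a history, physical examination, urinalysis and urine culture at day 7, symptom reporting to day 30, and reporting of all admissions and emergency visits.
- Patients are taught the symptoms of UTI and sepsis, and teleconsults are planned within 24 and 48 hours.
- A standard data collection form is mentioned but is not in the text at hand, so it may hold more fields.

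All of this stands. A reader might infer that these infections cannot be recorded or that the outcome cannot be derived, and the protocol does not support that. What remains is that none of these routes is stated to put each defining sign to every man in both arms. After day 7 capture depends on self-report, and the work-up for men with symptoms names a blood count, urinalysis and culture but no vital signs.

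Other tempting readings also fail:

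- **Seven of twelve signs are uncollected.** Three of those seven are recovered by temperature, heart rate and blood pressure once UTI is suspected. Moreover, one systemic sign is enough, so a missing rigors or delirium item matters only when no other listed sign is present.
- **The form loses a man with rigors and tachycardia but no urinary symptoms as a systemic UTI.** The outcome definition itself excludes him, and perfect data capture would not change that. For him the capture gap concerns sepsis.
- **Recording hematuria corrupts the outcome.** The protocol says that mild, self-limiting hematuria is not counted, so listing it does no harm if it is kept apart.
- **Misses always favour non-inferiority.** The checklist is the same in both arms and the design is described as blinded, so nothing places the misses in one arm. A single miss can act either way.

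It is also fair to say that the mismatch stems from the competing definitions. Settling those would not by itself change the form.

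**Conclusion.** The concern holds as a gap in systematic ascertainment. Four of twelve outcome signs are named in neither collection list, three more are gathered only once UTI is suspected, and sepsis is evaluated only behind UTI criteria that its own definition does not require. Affected events may be missed or misclassified; they are not impossible to record.

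The number of affected events cannot be estimated from the protocol and is probably small. It matters because only 0.7 to 0.8 events are expected per arm, so a single case, 1.7 points against a 5-point margin, can reverse the verdict in either direction. A consistent bias towards non-inferiority follows only if events are under-recorded in both arms and omission is truly worse.

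The conclusion rests on three assumptions: flank pain covers costovertebral angle pain; the unseen data form follows the checklist as described; and the interval is of Wald or Newcombe type. This should be corrected, but it does not invalidate the design or the sample size.

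**What to change.** 1. Rebuild the checklist from Description of Outcome Measures, with one item per defining sign. Keep hematuria as a separate item marked as not counting as infection.
2. Record temperature, heart rate, respiratory rate and blood pressure for every patient at the existing day-7 examination and at any symptomatic contact, so that sepsis can be assessed without a prior UTI label.
3. Reconcile the background criteria, the collection rules under Data to be gathered, the sepsis-evaluation rule under Criteria for withdrawing subjects, and the outcome definition. In particular, state whether systemic signs without local symptoms count towards the primary outcome. That would change the endpoint, so the choice is the sponsor's and should be made before unblinding.

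The cost is a revised form and routine vital signs at a visit that already includes a physical examination. No extra visit or laboratory test is needed. Patients already past day 7 will lack the added items, and the report should say so.

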Once the patient has given his signed consent, and patient is eligible to join the study, he will then be randomized into the experimental or control group using the online app https://www.random.org. The app generates a sequential list which prevents the investigator from learning allocation before a patient is registered into the study and from altering allocation afterwards, thus full concealment. Randomization will be performed by a research assistant not involved in the administration of treatments or data collection. The sequential list will be saved in a password protected file only accessible to the research assistant.. After a patient has been allocated, the group assignment will be permanent and unmodifiable. The randomization codes will be kept by the research assistant as well. Antibiotic or placebo will be administered by the stone center staff before the patient is put to sleep. The primary investigator will not be part of the biopsy procedure for blinding purposes.

Risks

One of the common side effects of prostate biopsy is infection. According to studies, 2% patients may experience mild disease not requiring hospitalization, and 1% may experience severe infections requiring hospitalization despite antibiotics. Based on literature, there will be no added risk of infection whether a patient is given antibiotics or not.

The most common side effect of antibiotic administration (Cefoxitin) is Diarrhea. Other rare side effects seen in less than 1% of patients given this drug includes Anemia, or decrease in hemoglobin, Increase in eosinophils in the blood, elevated liver enzymes, Decrease in platelets, and decrease in white blood cells. Patients who have allergies to antibiotics may also experience hypersensitivity reactions to this drug. There is also risk of alteration of the normal bacterial flora, which promotes antimicrobial resistance. This will decrease susceptibility of bacteria to antimicrobials making infections harder to treat.

Benefits

You will not receive direct benefits by participating in this study, however you may be spared from potential side effects of antibiotics. Furthermore, future prostate biopsy patients will benefit from enhanced guidelines on the need for prophylactic antibiotics to balance the risk of infection versus occurrence for antibiotic resistance.

Criteria for withdrawing subjects from the study and stopping the study as a whole

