All patients will be followed for 30 days for and assessed for post procedure infection. Initial assessment will be at 7 days post operatively with a history and physical exam. Symptoms of Urinary tract infection will be recorded. Urinalysis and urine culture will also be taken this time. Patients who are asymptomatic will be followed for 30 days, and will be asked to report symptoms of infection. All events within 30 days such as hospital admissions, emergency room visits, and non-infectious complications such as acute urinary retention will be reported. Mild and self limiting lower urinary tract symptoms, and hematuria will not be recorded as urinary tract infection as these are commonly seen after prostate biopsy. Patients who remain asymptomatic after the 30th post operative day will be treated as not having a post procedural infection. Persistent and severe lower urinary tract symptoms with associated fever will be assessed as having developed a post procedural infection, and patients will be treated accordingly. For patients who report symptoms on initial assessment, or within the 30 day time period, patients will be asked to contact primary investigator immediately for assessment, and will be asked to do a baseline Complete Blood Count, Urinalysis, and Urine Culture. Patients with mild to moderate illness (symptoms of fever and lower urinary tract symptoms such as those mentioned above, without urosepsis, circulatory failure and/or organ dysfunction may be treated as outpatient. Patients will be started on Ciprofloxacin 500mg 2x a day for 4 weeks, in line with recommendations of the European Association of Urology on treating Acute Prostatitis. Patients with marked debility and signs of sepsis as mentioned above, patients in whom there is uncertainty in diagnosis, and patients in whom there is concern about adherence to treatment, or patients unable to maintain oral hydration, or take oral medications, are patients in whom hospitalization will be advised. Baseline Complete Blood Count, Creatinine, Urinalysis, Urine Culture and Sensitivity and additional Blood culture and sensitivity will be done. Patients will be admitted in the private room of the hospital, and will be started on Broad Spectrum Antibiotics. Other additional medical management may vary depending on signs, symptoms and culture results. Hospital stay may vary as well, depending on signs and symptoms.

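### A febrile, non-septic patient meets two rules with different dispositions, which directly affects 30-day admissions and may affect the stopping counts

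*Protocol*

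**What the plan says.** **Data to be gathered.** After listing the SIRS signs to be collected in patients who show signs of urinary tract infection, the protocol states: "Patients with Fever, or 2 or more signs of SIRS will be advised admission immediately". Fever stands alone here, as an alternative to the SIRS criterion.

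**Follow-up procedures.** The group concerned is described as "Patients with mild to moderate illness (symptoms of fever and lower urinary tract symptoms such as those mentioned above". The sentence then sets a limit and gives a permission: "without urosepsis, circulatory failure and/or organ dysfunction may be treated as outpatient". An oral outpatient regimen follows. The section then lists who is advised to be hospitalised, beginning "Patients with marked debility and signs of sepsis as mentioned above, patients in whom there is uncertainty in diagnosis" and continuing with doubts about adherence and inability to take oral fluids or drugs. Fever alone is not on the list.

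**Stopping rule** (Criteria for withdrawing subjects and stopping the study). The study ends "if more than 2 patients develop mild biopsy infection, and more than 1 patient develop severe infections from the experimental group", and the conclusion is then fixed as a recommendation to give prophylaxis. Neither severity class is defined there.

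**Risks.** The literature rates are described as "2% patients may experience mild disease not requiring hospitalization, and 1% may experience severe infections requiring hospitalization despite antibiotics".

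**Description of Outcome Measures.** "Secondary outcome includes the following: 30 day hospital admissions, 30 day emergency room visits".

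**The concern.** The two sections dispose differently of a patient with fever and lower urinary tract symptoms who is not septic, and neither is said to take precedence. This is not a remote case: Follow-up procedures itself uses persistent, severe urinary symptoms with fever as its description of a post-procedural infection.

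Two quantities are exposed. The first is the secondary outcome of 30-day admissions, which counts whoever is admitted. The second, less directly, is the pair of stopping counts: the only descriptions of mild and severe that accompany the rates behind the limits turn on whether hospitalisation is required. Consistent safety management is also at stake in a trial that withholds prophylaxis from one arm.

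**Working it through.** **1. The texts side by side, for a patient with fever, urinary symptoms and no sepsis**

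| Section | What it implies |
|---|---|
| Data to be gathered | Immediate advice to be admitted |
| Follow-up procedures, outpatient sentence | Outpatient care permitted; illness classed as mild to moderate |
| Follow-up procedures, hospitalisation list | Fever alone not listed |
| Background, definition of post-biopsy infection | Fever listed as a feature of severe urinary tract infection |
| Risks, and the stopping section | Severe described as requiring hospitalisation |

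Disposition is contradictory, and so is the severity label: fever appears under severe in the Background and under mild to moderate in Follow-up procedures.

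**2. The plan's own figure**

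Inputs from Sample Size and Sampling Technique: 1.35% with prophylaxis, 1.22% without, margin 5%, 80% power, 90% confidence interval (one-sided 5%).

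n = [p₁(1−p₁) + p₂(1−p₂)] × (z₀.₉₅ + z₀.₈₀)² / (margin − (p₂ − p₁))²
= (0.01332 + 0.01205) × 6.183 / 0.0513²
= 59.6, so 60 per arm.

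The stated 60 is reproduced. It is not in dispute and serves below as the denominator of the stopping counts.

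**3. Expected counts in the experimental arm**

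Mild: 60 × 0.02 = 1.2. Severe: 60 × 0.01 = 0.6. With counts this low, relabelling one or two patients can decide whether a limit is passed.

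**4. Sensitivity of the stopping counts to the label**

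Let f be the share of mild cases that become severe because they are febrile and admitted. The documents do not give f, so the full range is shown. The mild rate is 0.02(1−f) and the severe rate is 0.01 + 0.02f.

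- P(more than 1 severe) = 1 − (1−p)⁶⁰ − 60p(1−p)⁵⁹. At p = 0.01 this is 1 − 0.547 − 0.332 = 0.121. At p = 0.03 it is 1 − 0.161 − 0.298 = 0.541.
- P(more than 2 mild) is the binomial probability of 3 or more. At p = 0.02 it is 0.119.
- P(both) is the exact trinomial sum over 3 or more mild and 2 or more severe.
- P(either) = P(mild limit) + P(severe limit) − P(both). At f = 0 this is 0.1187 + 0.1212 − 0.0135 = 0.226.

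| f (assumed) | More than 2 mild | More than 1 severe | Either | Both (as worded) |
|---|---|---|---|---|
| 0 | 11.9% | 12.1% | 22.6% | 1.35% |
| 0.25 | 6.1% | 22.7% | 27.6% | 1.32% |
| 0.5 | 2.2% | 33.8% | 35.3% | 0.72% |
| 1 | 0% | 54.1% | 54.1% | 0% |

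The label moves the result under either reading of the rule, in opposite directions: upward if either limit suffices, downward if both are needed.

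**The case against.** **The overlap is limited, and the wording is soft.** The outpatient sentence excludes patients with urosepsis, circulatory failure or organ dysfunction. One sepsis definition in the Background combines temperature above 38°C, among other signs, with pathogen growth in urine or blood. On one reading of it, a febrile culture-positive patient is septic and would be hospitalised under both sections. The Background also gives a SOFA-based definition, so this is not certain. One text only advises admission and the other only permits outpatient care. These points stand and confine the conflict to the non-septic febrile patient, but they do not remove it: for that patient one section advises immediate admission, while the other omits him from its hospitalisation list.

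**The link to stopping is inferred.** The hospitalisation wording describes literature rates and speaks of infections that require admission, not of patients who were admitted. The Background's list classes by symptom, wherever the patient is treated. This stands. The underlying gap is that mild and severe are undefined for the rule; the fever conflict is one contributor.

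**A reader might infer that the choice of section moves the chance of stopping from 27% to 54%.** Those are the chances of 3 or more, and of 2 or more, infections in 60 at a 3% total rate. The documents do not support that reading. It needs every infection to be febrile, although localised infection is defined under Description of Outcome Measures without fever. It counts the 1% severe infections as mild in the lower figure. It also treats the limits as separate triggers, although they are joined by 'and'. With all infections in one class, the rule as worded could never be met: 0% in both cases.

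**Bias between arms is not evident.** Patients and doctors are described as blinded, and symptomatic patients contact the primary investigator, who assesses them with the consultant. This reduces, but does not exclude, inconsistent handling across centres.

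**Conclusion.** The contradiction is real and lies in current text, for a febrile, non-septic patient with urinary symptoms. Its effect on the 30-day admissions outcome and on consistent safety management is direct. Its size there cannot be computed, because the febrile share is not given.

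The effect on stopping is possible rather than established. With 60 patients, the protocol's 2% and 1% rates and an assumed reclassified share from 0 to 1, the chance of crossing either limit runs from 23% to 54%, and the chance of crossing both from 1.4% to 0%. It would go too far to say that the protocol makes the same patient severe by one section and mild by the other for stopping purposes, since the stopping rule does not tie its classes to actual admission.

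The incidence of urinary tract infection and sepsis, the primary outcome, does not depend on where a patient is treated. The point should be settled by amendment but ranks below the defects that must be fixed before the trial can be relied on.

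**What to change.** Reconcile Data to be gathered and Follow-up procedures into one fever rule that applies at both centres. Which disposition is right is a clinical matter for the sponsor.

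In the same amendment, state whether a febrile, non-septic infection counts as mild or as severe for the stopping rule. Define that class independently of where the patient was treated, and align it with the Background's list of features of severe infection.

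The cost is protocol wording only: no additional patients, tests or staff.
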